3.7.3. Adverse Events of Special Interest

Adverse events of special interest (AESIs) will be summarized by Preferred Term and by prior ALKS 5461 exposure and overall during treatment period for the Safety Population / Post-discontinuation Safety Population for any TEAEs or PDEAEs of special interest. The following summaries will be created for AESI:

- TEAEs associated with abuse potential
- TEAEs associated with dependence
- PDEAEs associated with withdrawal
- TEAEs associated with suicidal ideation and behavior
- TEAEs associated with hypomania / mania
- TEAEs associated with central nervous system (CNS) depression and sedation
- TEAEs associated with respiratory depression
- TEAEs associated with orthostasis / hypotension
- TEAEs associated with hypersensitivity

- TEAEs associated with slowing of ventricular repolarization
- TEAEs associated with hepatic effects
- TEAEs associated with sexual dysfunction

TEAEs associated with abuse potential will be presented by Adhoc System Organ Class and Preferred Term, where Adhoc System Organ Class is manually classified by Alkermes medical director as 3 categories: abuse behavior, euphoria related, and non-specific.

TEAEs associated with dependence will be presented for subjects with any exposure, ≥4 weeks exposure, and <4 weeks exposure, respectively.

PDEAEs associated with withdrawal will be presented for subjects with any exposure, ≥4 weeks exposure, and <4 weeks exposure, respectively. AESIs associated with withdrawal are PDEAEs that occur from >2 to 16 days post last dose as this is the period during which physiological opioid withdrawal presents by considering half-lives of both BUP and SAM.

Supportive AE listings will be provided for each special interest group. Narratives will be provided for clinically meaningful events within each AESI group.

3.7.4. Clinical Laboratory Parameters

Laboratory parameters will be presented in conventional units. Only scheduled laboratory assessments will be included in the summaries of mean and change from baseline descriptive analyses. Laboratory assessments from both scheduled and unscheduled visits will be included in outlier analyses. Outlier analyses will not include post-discontinuation assessments. All laboratory data will be included in the listings. Parameter order for summary tables and listings will be by system (renal, hepatic, etc.).

3.7.4.1. Descriptive Analysis of Laboratory Parameters

Numerical laboratory results (baseline and change from baseline) for chemistry and hematology parameters and urinalysis (pH and Specific Gravity) for each visit during the entire study (including last assessment during treatment period and visits in Post-discontinuation Safety Period) will be summarized (number of subjects, mean, SD, median, minimum, and maximum) by prior ALKS 5461 exposure and overall for the Safety Population.

In addition, baseline and post-baseline observed values (lowest, highest, last assessment during treatment period), and change from baseline to lowest, highest and last assessment values during the treatment period for chemistry and hematology parameters, urinalysis (pH and Specific Gravity), will be summarized by prior ALKS 5461 exposure and overall for the Safety Population.

The following graphical displays for laboratory parameters (chemistry, hematology, and urinalysis) will be presented during the entire study (including last assessment during treatment period and Post-discontinuation Safety Period) by prior ALKS 5461 exposure and overall for the Safety Population:

- Line graphs for mean change from baseline along with the corresponding standard error (SE; including Post-discontinuation Safety Period)
- Box-and-Whisker figures for baseline and post-baseline observed values (lowest, highest, last assessment during treatment period)
- Box-and-Whisker figures for change from baseline to the lowest post-baseline value, the highest post-baseline value, and the last scheduled post-baseline value during treatment period
- Scatter plots for baseline and post-baseline observed values (lowest, highest, last assessment during treatment period)

3.7.4.2. Outlier Analyses of Laboratory Parameters

The number and percentage of subjects with values considered potentially clinically significant (PCS) occurring at any post-baseline visit during treatment period for selected parameters will be summarized. For PCS, the summary will be provided by prior ALKS 5461 exposure and overall for the Safety Population. These analyses do not include Post-discontinuation Safety Period.

Clinical laboratory test values, scheduled or unscheduled, will be considered PCS if they meet the PCS criteria listed in Table 4. The percentage will be calculated relative to the number of subjects with available non-PCS baseline values with respect to the specific criterion and at least 1 post-baseline assessment. The numerator is the total number of subjects with a non-PCS baseline value with respect to the specific criterion and at least 1 post-baseline PCS value. A supportive listing will present all values for a parameter for subjects with at least 1 PCS value for that parameter.

Shift tables for shift from within normal reference limits / high to low and shift from within normal reference limits / low to high during treatment period will be provided for chemistry, hematology, and urinalysis parameters with conventional reference limits (limits provided by the performing laboratories) by prior ALKS 5461 exposure and overall for the Safety Population. For parameters which have gender and / or age specific limits, the categories will be based on the specific limits. High is defined as values greater than the upper limit of the reference range (ULRR). Low is defined as values less than the lower limit of the reference range (LLRR). Normal reference limits is defined as values within normal range. The analysis population consists of subjects in the Safety Population with a baseline value outside the specific shift direction. All laboratory values collected during the treatment period will be considered in this analysis.

The percentages will be calculated for the shift summary as follows:

- For the shifts from within normal reference limits / high to low: the numerator is defined as the number of subjects with a post-baseline result below the LLRR, and the denominator is defined as the number of subjects with a baseline value within the limits or above the ULRR.
- For the shifts from within normal reference limits / low to high: the numerator is defined as the number of subjects with a post-baseline results above the ULRR, and the denominator is defined as the number of subjects with a baseline value within the limits or below the LLRR.

Pregnancy and drug screening data will be listed. For urinalysis, rate of abnormalities at any post-baseline visit during treatment period will be summarized.

 Table 4:
 Potentially Clinically Significant Abnormal Laboratory Values

Category	Parameter	Criteria		
Hematology	Eosinophils	$>1.0x10^3/\mu L$		
	Hematocrit	≤32% and 3 point decrease from baseline (Female) ≤37% and 3 point decrease from baseline (Male)		
	Hemoglobin	≤9.5 g/dL (Female) ≤11.5 g/dL (Male)		
	Leukocytes	$\leq 2.8 \times 10^{3} / \mu L$ $\geq 16 \times 10^{3} / \mu L$		
	Neutrophils, Absolute	$<1.5x10^{3}/\mu L$		
	Platelets	$<75.1 \times 10^{3} / \mu L$ $\geq 700 \times 10^{3} / \mu L$		
Chemistry	Alanine Aminotransferase	≥3xULRR		
	Albumin	<2.5 g/dL		
	Alkaline Phosphatase	≥3xULRR		
	Aspartate Aminotransferase	≥3xULRR		
	Bicarbonate	<15 mmol/L >31 mmol/L		
	Blood Urea Nitrogen (BUN)	>30 mg/dL		
	Calcium	<8.2 mg/dL >12 mg/dL		
	Chloride	≤90 mmol/L ≥118 mmol/L		
	Creatine Phosphokinase	>3xULRR		
	Creatinine	≥2 mg/dL		

Table 4: Potentially Clinically Significant Abnormal Laboratory Values (Continued)

Category	Parameter	Criteria
	Gamma Glutamyltransferase	≥3xULRR
	Glucose	<50 mg/dL
		>200 mg/dL
	HDL Cholesterol	≤30 mg/dL
	Lactate Dehydrogenase	>3xULRR
	LDL Cholesterol	≥160 mg/dL
	Phosphate	<2 mg/dL >5 mg/dL
	Potassium	<3 mmol/L >5.5 mmol/L
	Prolactin	>1xULRR
	Sodium	<130 mmol/L >150 mmol/L
	Total Bilirubin	≥2 mg/dL
	Total Cholesterol	>300 mg/dL
	Triglycerides	≥120 mg/dL (Female) ≥160 mg/dL (Male)
	Uric Acid	>9 mg/dL >8 mg/dL (Female) >10 mg/dL (Male)
Urinalysis	Glucose Protein	at least 2+

Abbreviations: BUN=blood urea nitrogen; HDL=high density lipoproteins; LDL=low density lipoprotein; ULRR=upper limit of referene range

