3.2. Study Population

3.2.1. Definitions of Analysis Populations (Analysis Sets)

Safety Population consists of all subjects who receive at least 1 dose of study drug in the ALK5461-208 study.

An AE will be considered as a treatment emergent adverse event (TEAE) if it starts or worsens (if present at baseline) on or after the baseline during treatment period. An AE will be

considered as a post-discontinuation emergent adverse events (PDEAE) if it starts or worsens after the last dose date plus 1 day.

Post-discontinuation Safety Population consists of subjects in the Safety Population who have at least 1 post-discontinuation measurement. There will be two Post-discontinuation Safety Populations, one is used to analyze PDEAE, and the other is to analyze COWS, grouped by whether having had exposure to study drug in a prior controlled trial or had no prior exposure.

Post-discontinuation Safety Population for PDEAE consists of subjects who received at least 1 dose of study drug, and met one of the following criteria:

- Subjects who entered the Post-discontinuation Period and had a Post-discontinuation Visit
- Subjects who did not enter the Post-discontinuation Period, but had at least 1 PDEAE reported
- Subjects who died after either completing the treatment or having an Early Termination (ET) Visit

Post-discontinuation Safety Population for COWS consists of subjects who received at least 1 dose of study drug, had an adequate COWS baseline (defined as end of treatment [EOT] COWS assessment) and had at least 1 post-EOT COWS assessment, where an adequate EOT COWS is defined as having been performed within (≤) 2 days of last dose of study drug.

Full Analysis Set (FAS) consists of subjects in the Safety Population who have at least 1 post-baseline complete MADRS assessment.

The baseline for efficacy endpoints is defined as the last non-missing observation on or before the date of baseline visit (Visit 2) of ALKS 5461-208 study for subjects who are new to ALKS 5461 (ie, De Novo, PLI Failures, and Continuing Subjects who received placebo in antecedent study); or the last non-missing observation on or before the first dose of ALKS 5461 in antecedent study for Continuing Subjects who received any dose of ALKS 5461 (i.e., ALKS 5461 0.5/0.5, ALKS 5461 1/1, or ALKS 5461 2/2) in antecedent study.

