This analysis population consists of safety population with non-missing baseline and at least 1 post-baseline assessment during treatment period. The percentage will be calculated for the treatment emergent suicide-related event summary. The numerator is defined as the number of subjects with a non-missing baseline and a post-baseline C-SSRS assessment meeting the treatment emergent suicide-related numerator criteria defined in Table 11, and the denominator is defined as the number of subjects with a non-missing baseline and at least 1 post-baseline C-SSRS assessment meeting the treatment emergent suicide-related denominator criteria defined in Table 11 during treatment period.

Table 11: Treatment Emergent Suicide-related Events for Analysis

Treatment Emergent Suicide- related Events	Denominator Criteria	Numerator Criteria
Increase in Suicidal Ideation from Baseline	Baseline suicidal ideation ("No" to all ideation items 1- 5, or "Yes" to any ideation item ≤4 and "No" to item 5)	Baseline suicidal ideation ("No" to all ideation items 1-5, or "Yes" to any ideation item ≤4 and "No" to item 5)
		Post-baseline (increase in suicidal ideation severity from baseline at any post-baseline visit)
Emergence of Serious Suicidal Ideation	Baseline suicidal ideation ("No" to all ideation items 1-5, or "Yes" to any ideation item≤3 and "No" to items 4 and 5)	Baseline suicidal ideation ("No" to all ideation items 1-5, or "Yes" to any ideation item ≤3 and "No" to items 4 and 5) Post-baseline ("Yes" to ideation item 4 or 5 at any post-baseline visit)
Emergence of Serious Suicidal Ideation in Subjects with no Suicidal Ideation at Baseline	Baseline ideation ("No" to all ideation items 1-5)	Baseline ideation ("No" to all ideation items 1-5) Post-baseline ("Yes" to ideation item 4 or 5 at any post-baseline visit)
Decrease in Suicidal Ideation from Baseline	Baseline ideation ("Yes" to any ideation items 1-5)	Baseline ideation ("Yes" to any ideation items 1-5) Post-baseline (decrease in suicidal
		ideation severity at any post- baseline visit compared to severity at baseline)
Emergence of Suicidal Behavior in Subjects with no Suicidal Behavior	Baseline behavior ("No" to all behavior items 6-10)	Baseline behavior ("No" to all behavior items 6-10)
at Baseline		Post-baseline behavior ("Yes" to any behavior items 6-10 at any post-baseline visit)

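### The laboratory shift denominators in SAP 3.7.4.2 require only a qualifying baseline, so a subject with no post-baseline value counts as having no shift

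*SAP*

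**What the plan says.** SAP Section 3.7.4.2 contains two kinds of laboratory percentage with different denominator rules.

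- **PCS percentage.** It is calculated "relative to the number of subjects with available non-PCS baseline values with respect to the specific criterion and at least 1 post-baseline assessment". Both a baseline and a post-baseline condition apply.
- **Shift to low.** In the numerator definition, "the numerator is defined as the number of subjects with a post-baseline result below the LLRR"; in the denominator definition, "the denominator is defined as the number of subjects with a baseline value within the limits or above the ULRR".
- **Shift to high.** Here "the denominator is defined as the number of subjects with a baseline value within the limits or below the LLRR".
- **Population for both shift tables.** "The analysis population consists of subjects in the Safety Population with a baseline value outside the specific shift direction". The Safety Population itself (SAP 3.2.1) "consists of all subjects who receive at least 1 dose of study drug in the ALK5461-208 study", so it brings in no post-baseline condition either.

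For comparison, SAP 3.7.7 on treatment-emergent suicide-related events states: "This analysis population consists of safety population with non-missing baseline and at least 1 post-baseline assessment during treatment period". The COWS population in SAP 3.2.1 likewise needs an assessment after the end-of-treatment one.

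**The concern.** The numerator can be reached only by someone with a post-baseline result, while the denominator admits people who have none. Those people are in effect scored as not having shifted, although nothing was observed. The error can go only one way: the printed rate is never higher than the rate among subjects who could be evaluated. Its size can differ between analytes, and between the prior-exposure and no-prior-exposure columns if early departure differs between them. Long-term safety is the study's only stated objective, so a rule that can only lower laboratory shift rates deserves correction even in descriptive tables.

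**Working it through.** **No plan figure to reproduce.** The documents state no expected shift rate, and no sample-size or power figure bears on this point.

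**Formula.** Let
- B = subjects with a qualifying baseline for the parameter and direction;
- f = the share of B with no on-treatment post-baseline value (not in the documents; assumed);
- E = B(1 − f) = evaluable subjects;
- x = subjects who shift, all of whom lie within E.

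The SAP rate is x/B and the evaluable rate is x/E. Hence x/B = (x/E)(1 − f). The relative reduction is exactly f and does not depend on B.

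**Numbers.** Take B = 1,500 (planned enrolment, SAP Section 2, used only as a convenient count) and an evaluable rate of 10%.

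| f (assumed) | E | x | SAP rate x/B | Evaluable rate x/E |
|---|---|---|---|---|
| 0% | 1,500 | 150 | 10.0% | 10.0% |
| 2% | 1,470 | 147 | 9.8% | 10.0% |
| 8% | 1,380 | 138 | 9.2% | 10.0% |
| 20% | 1,200 | 120 | 8.0% | 10.0% |
| 30% | 1,050 | 105 | 7.0% | 10.0% |

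**Where f could come from.** The schedule is in protocol Tables 2 and 4.
- Most analytes: first repeat at Day 8, so f should be small.
- HbA1c: first repeat at Visit 8 (Day 99) or ET.
- Prolactin: first repeat at Visit 10 (Day 183) or ET.
- Thyroid-stimulating hormone: drawn at Visit 1 only. If it were put in the shift tables, the rule would print 0/B = 0% for a test with no scheduled repeat.

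Subjects who stop early are invited to an ET visit but may decline, in which case the site tries to reach them by telephone (protocol 7.3 and 8.2). A telephone call yields no blood sample. Follow-up laboratory results do not fill the gap, because the shift tables cover the treatment period and SAP 3.7.4 leaves post-discontinuation values out of outlier analyses.

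**Prolactin as a direct comparison.** SAP Table 4 defines PCS prolactin as above 1 × ULRR. The shift table defines high as above the ULRR. A non-PCS baseline is thus the same as a baseline within or below the limits, and the two numerators count the same subjects. If the PCS condition is read as an assessment of the parameter in question, the denominators are E for PCS and B for the shift. With f = 20% in the table above, one table would print 120/1,200 = 10.0% and the other 120/1,500 = 8.0% for the same event.

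**The case against.** Four points can fairly be made for the plan.

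1. *The general rule may cover it.* SAP 3.7.1 and 7.1 say that summaries use observed data and that missing values are not imputed. A programmer might therefore require a baseline and post-baseline pair, and the programming specifications and table shells are separate documents. This softens the point, but a general convention does not override a denominator spelled out for this table.
2. *The SAP rate is itself interpretable.* It is the share of treated subjects with an eligible baseline in whom a shift was observed, a lower bound. That is true, and the status of unsampled subjects is unknown. But it is not the basis used for PCS or C-SSRS, and the SAP gives no reason for the difference.
3. *The two tables differ anyway.* For most parameters the PCS thresholds are not the reference limits, so the baseline groups differ by design. This stands: a reader might infer that the missing condition makes the PCS and shift tables disagree throughout, or that the fix would align them. The documents support that only for prolactin.
4. *Few subjects may be affected.* This also stands. A reader might infer that shift rates are in fact diluted, or that everyone who leaves before Week 26 lacks a repeat prolactin value. Neither follows. If every qualifying subject has a repeat value, f = 0 and the rules agree. Prolactin is also drawn at ET, and unscheduled on-treatment results count, so it is lost only for those who leave before Visit 10, skip ET and have no unscheduled result.

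**Conclusion.** The inconsistency is in the text and its direction is certain: taken literally, the shift rule can lower the reported rates but never raise them. Its size cannot be derived from the documents, and every value of f used here is an assumption. A reader might also infer that the study's conclusions are affected. The documents do not support that: the study has no reference therapy, the tables are descriptive, and no test or sample size depends on them. This is a minor point, worth correcting because the correction is simple and removes a one-sided error from safety tables.

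**What to change.** In SAP 3.7.4.2, add *and at least 1 post-baseline value of that parameter during the treatment period* to the shift analysis population and to both shift denominators. State also that parameters with no scheduled post-baseline test, such as thyroid-stimulating hormone, are left out of the shift tables. The cost is one phrase in three places, one clarifying sentence, and a matching check of the table programs. No new data are needed, and I see no real drawback.

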≥10xULRR	Baseline <10xULRR	Baseline ≤1xULRR		
≥20xULRR	Baseline <20xULRR			

Abbreviations: ULRR=upper limit of reference range

Table 6: Shift Criteria and Denominator for Aspartate Aminotransferase (AST)

	Denominator			
AST Elevations During Treatment Period	All Subjects	Subjects with Baseline Values ≤1xULRR	Subjects with Baseline Values >1xULRR	
≥3xULRR	Baseline <3xULRR		Baseline >1xULRR	
≥5xULRR	Baseline <5xULRR	Dagalina / LyLIL DD		
≥10xULRR	Baseline <10xULRR	Baseline ≤1xULRR		
≥20xULRR	Baseline <20xULRR			

Abbreviations: ULRR=upper limit of reference range

Table 7: Shift Criteria and Denominator for Total Bilirubin (TBILI)

Total Bilirubin Elevations During Treatment Period	Denominator
≥2xULRR	All Subjects with Baseline <2xULRR
≥2xULRR	Baseline ≤1xULRR
≥2xBaseline	Baseline >1xULRR

Abbreviations: ULRR=upper limit of reference range

3.7.5. Vital Signs

Vital signs (supine systolic and supine diastolic blood pressure, heart rate, respiratory rate, temperature, weight, and BMI) will be summarized for baseline and change from baseline (BMI baseline only) by prior ALKS 5461 exposure and overall for the Safety Population, and will include post-discontinuation assessments.

In addition, baseline and post-baseline observed values (lowest, highest, last assessment during treatment period), and change from baseline to lowest, highest and last assessment values during treatment period for vital sign parameters will be summarized by prior ALKS 5461 exposure and overall for the Safety Population, and will not include post-discontinuation assessments.

The following graphical displays for vital sign parameters will be presented by prior ALKS 5461 exposure and overall for the Safety Population:

- Line graphs for mean change from baseline along with the corresponding SE (including Post-discontinuation Safety Period)
- Box-and-Whisker figures for baseline and post-baseline observed values (lowest, highest, and last assessment during treatment period)
- Box-and-Whisker figures for change from baseline to the lowest post-baseline value, the highest post-baseline value, and the last scheduled post-baseline value during treatment period
- Scatter plots for baseline and post-baseline observed values (lowest, highest, and last assessment during treatment period)

Vital signs will also be evaluated using PCS criteria as indicated in Table 8 and summarized by prior ALKS 5461 exposure and overall for the Safety Population. Post-discontinuation assessments will not be included in this analysis.

 Table 8:
 Potentially Clinically Significant Abnormal Vital Sign Values

Parameter	PCS Criteria	
Temperature	Hyperthermia: ≥38.1°C	
	Hypothermia: ≤35.0°C	
Supine Systolic Blood Pressure	Low: ≤90 mm Hg and decrease ≥20 mm Hg	
	High: ≥140 mm Hg and increase ≥20 mm Hg	
Supine Diastolic Blood Pressure	Low: ≤50 mm Hg and decrease ≥10 mm Hg	
	High: ≥90 mm Hg and increase ≥10 mm Hg	
Heart Rate	Low: ≤50 bpm and decrease ≥15 bpm	
	High: ≥100 bpm and increase ≥15 bpm	
Respiratory Rate	Low: <12 breaths per minute	
	High: >25 breaths per minute	
Body Weight	Decrease from baseline ≥7%	
	Increase from baseline ≥7%	

A supportive listing will present for subjects and parameter for cases where at least 1 value was potentially significant.

3.7.6. Electrocardiograms

Electrocardiogram (ECG) parameters (heart rate, RR interval, PR interval, QRS interval, QT interval, and QTcF [QT interval corrected using Fridericia's method]) will be summarized (baseline and change from baseline) for each visit during the entire study, including last assessment during treatment period and post-discontinuation assessments.

In addition, baseline and post-baseline observed values (lowest, highest, last assessment during treatment period), and change from baseline to lowest, highest and last assessment values during treatment period for ECG parameters will be summarized by prior ALKS 5461 exposure and overall for the Safety Population. These analyses will not include post-discontinuation values.

The following graphical displays for ECG will be presented by prior ALKS 5461 exposure and overall for the Safety Population:

- Line graphs for mean change from baseline along with the corresponding SE (including Post-discontinuation Safety Period)
- Box-and-Whisker figures for baseline and post-baseline observed values (lowest, highest, last assessment during treatment period)
- Box-and-Whisker figures for change from baseline to the lowest post-baseline value, the highest post-baseline value, and the last scheduled post-baseline value during treatment period
- Scatter plots for baseline and post-baseline observed values (lowest, highest, last assessment during treatment period)

ECG will be evaluated using PCS criteria as indicated in Table 9 by prior ALKS 5461 exposure and overall for the Safety Population. These analyses will not include post-discontinuation assessments.

 Table 9:
 Potentially Clinically Significant Abnormal ECG Values

ECG Parameter	PCS Criteria	
PR Interval	High: ≥220 msec	
QRS Interval	High: ≥120 msec	
QTcF	Low: <330 msec High: >450 msec; >480 msec; >500 msec	
	Only cumulative incidence above the indicated limits	
QTcF	Change from baseline increase/decrease >30 msec	
	Change from baseline increase/decrease >60 msec	
Heart Rate	Low: ≤50 bpm and decrease ≥15 bpm	
	High: ≥100 bpm and increase ≥15 bpm	

A supportive listing will present all values for a parameter for subjects with at least 1 PCS value for that parameter.

